Aim 2 will compare change in length-for-age Z-score (ΔLAZ) between the control group and intervention from enrolment to 90 days. We have estimated that we will have 80% power to detect at least a 0.04 difference in mean ΔLAZ between study groups using a two-sided t-test to compare the difference in mean change in LAZ between two groups with $\alpha=0.05$ and standard deviation (SD) of 0.7 in both groups. This is comparable to results observed in the Global Enterics Multicenter Study (GEMS). As the SD of the difference in ΔLAZ has been

¹ Jennison C, Turnbull BW. Group Sequential Methods with Applications to Clinical Trials. Chapman and Hall/CRC,1999 (page 150)

shown to vary, Table 1 below outlines the minimum detectable difference in Δ LAZ with varying SD.

Table 1. Sample size and minimum detectable difference in Δ LAZ with varying power and standard deviation

Scenario	Minimum detectable difference in mean Δ LAZ	Standard deviation (equal SD per group)	Sample size (per group) at 90% power	Sample size (per group) at 80% power
A	0.06	0.7	2862	2138
		0.6	2103	1571
		0.5	1461	1092
B	0.05	0.7	4120	3078
		0.6	3028	2262
		0.5	2103	1571
C	0.04	0.7	6437	4809
		0.6	4730	3533
		0.5	3285	2454

We have estimated that we will have 90% power to detect at least a 0.04 difference in mean Δ LAZ between study groups (5,750 children per group) using a two-sided t-test to compare the difference in mean Δ LAZ between two groups with $\alpha=0.05$ and standard deviation (SD) of 0.6 in both groups. Assuming 50% of children will be less than 12 months of age at enrolment (2,85085 infants per group), we will have 90% power to detect at least a 0.06 difference in mean Δ LAZ between study groups comprised of infants and separately, between study groups comprised of toddlers (12-23 months). As a point of reference, combined across all sites in GEMS, Moderate to Severe Diarrhoea (MSD) cases lost 0.04 more in LAZ, on average, than controls among infants ($p<0.001$) and among toddlers, MSD cases lost 0.10 more in LAZ than controls ($p<0.001$).

For secondary objectives 6-7, the number of children enrolled in the AMR sub-study was determined for comparison of azithromycin resistance prevalence between the azithromycin and placebo arm on DAY 90 and DAY 180. The analysis is planned to be done regionally (separately for Asia and Africa), because we assume similarity in AMR within a region but differences between the two regions. Hence, all the numbers below indicate numbers / region.

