4.4 Sensitivity analyses examining potential baseline imbalances

We will report baseline characteristics of participants by trial allocation arm (Table 1), we will examine imbalance by trial arm, accepting that these arose by random chance, and will not conduct hypothesis tests for difference by allocation arm. However we will include any apparent imbalances in sensitivity analyses for all primary and secondary outcomes. In sensitivity analyses, we will include as model covariates characteristics which on univariable analysis are associated with the outcome of interest with a p-value <0.10 . If the point-estimates for the unadjusted and adjusted analyses of the primary outcomes differ by more than 10%, the adjusted analysis will be presented as primary.

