9.1 Primary outcome 1 - 180 day Mortality

We will report the unadjusted risk ratio (RR) of all-cause death by trial allocation arm, which will be the number of deaths over number of persons in each trial allocation arm, and report either a χ^2 -test of $[(\text{death/placebo})/(\text{death/azithromycin})]$ or a Z-test of the $\log[(\text{death/placebo})/(\text{death/azithromycin})]$.

We will examine the 180-day fatality by randomized treatment groups using log-binomial mixed effects models to calculate the risk ratio and 95% confidence bound. Models will include trial site indicators as fixed effects to account for the randomization schema. The primary analysis would only include site as this is the stratified randomization factor. Fatality effect estimates will be presented in Table 2.

Regression model for the outcome of mortality in the ABCD trial will be defined as the following log-binomial mixed effects model:

$$\log Pr(Y_i = 1) = \beta_{0c} + \beta_1 C_i + \beta_2 Z_i \times 1_{\{t>t_0\}} + \varepsilon_i$$

– Model 1

Where

$$Y_i = \begin{cases} 1 & \text{died} \\ 0 & \text{alive at day 180} \end{cases}$$

And

$$\beta_{0c} = \beta_0 + b_c$$

Under this definition we are accounting for clustering at clinic level. The b term is a random effects for the c^{th} clinic, and take account of the variance due to clustering within clinic.

The term $\beta_1 C_i$ is the fixed effect of country, with C_i representing the country of enrolment for child i .

The term $\beta_2 Z_i$ is the fixed effect of azithromycin, with Z_i representing the treatment allocation for child i where

$$Z_i = \begin{cases} 1 & \text{azithromycin} \\ 0 & \text{placebo} \end{cases}$$

The term ε_{ij} is the variance component due to random error for child i at time j .

Now if $\mu_i = \log Pr(Y_i = 1)$ then Y is distributed as

$$Y_i \sim \text{Binomial}(\mu_i | b_c)$$

and Relative Risk of death by $Z_i = \exp(\beta_1)$

Extending Model 1 to admit child level covariates, we have:

$$\log Pr(Y_i = 1) = \beta_{0c} + \beta_1 C_i + \beta_2 Z_i \times 1_{\{t > t_0\}} + \beta_3 X_{ij} + \varepsilon_{ij}$$

- Model 2

Where X_{ij} is the vector of effect-modifying covariates of child i at time j :

$$X_{ij} = \begin{cases} \text{age category } (< 6m, 6 - 11m, \geq 12m) \\ \quad + \text{Sex} \\ \quad + \text{Reason for enrolment} \quad \quad \quad \text{(See Section 4.5)} \\ \quad + \text{Wealth quintile} \end{cases}$$

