9.2 Primary outcome 2 - Change in Length-for-age z-score

The group means at baseline and endline and the mean ΔLFAZ will be presented by treatment group in Table 3. We will use generalized linear mixed models with ΔLAZ as the response variable and treatment group, fixed effects for study site and variable effects for child (which accounts for baseline LAZ) and clinic as the explanatory variables.

The primary analysis for this variable will only include the site since this is the stratified randomization..

Regression model for the outcome change from baseline in length for age Z-score (Δ LFAZ) in the ABCD trial is defined as the following linear mixed-effects model:

$$Y_{ij} = \beta_{0_{c_i}} + \beta_1 C_i + \beta_2 Z_i \times 1_{\{j=1\}} + \varepsilon_{ij} \quad \text{- Model 3}$$

Y_{ij} is Δ LFAZ in child i at time j , where

$$j = \begin{cases} 1 & \text{day 90} \\ 0 & \text{enrollment} \end{cases}$$

$\beta_{0_{c_i}}$ is the random effect of child i at clinic c , where

$$\beta_{0_{c_i}} = \beta_0 + b_{c_i} + b_{0_i}$$

Under this definition we are accounting for clustering at clinic level and at child level. The b terms are random effects for the c^{th} clinic and the i^{th} child, and take account of the variance due to clustering within clinic or over time in a given child. The latter is effectively also an adjustment for baseline LFAZ and WFAZ for that child. Should these models not converge, we will allow clinic to remain the random effect, but adjust for baseline LFAZ as a fixed effect.

The term $\beta_1 C_i$ is the fixed effect of country, with C_i representing the country of enrolment for child i .

The term $\beta_2 Z_i$ is the fixed effect of azithromycin, with Z_i representing the treatment allocation for child i where

$$Z_i = \begin{cases} 1 & \text{azithromycin} \\ 0 & \text{placebo} \end{cases}$$

The term ε_{ij} is the variance component due to random error for child i at time j .

Participants whose Day 90 visit occurred outside the protocol defined window will be included in the Intention to Treat Analysis. Sensitivity analysis will take account of the time varying nature of this visit by fitting a model that allows the effect of azithromycin to vary as a function of time is:

$$Y_{ij} = \beta_{0_{c_i}} + \beta_1 C_i + \beta_2 Z_i \times 1_{\{t>t_0\}} + \beta_3 Z_i t_{ij} \times 1_{\{t>t_0\}} + \varepsilon_{ij}$$

- Model 4

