Model 4 allows for a proportional effect of fixed magnitude (parameter β_2) *and* for a time-varying effect (parameter β_3).

Under Model 2 the term $\beta_{0_{ci}}$ is the random effect of child i at clinic c , as it was above, but where

$$\beta_{0_{ci}} = \beta_0 + b_{ci} + b_{0i} + b_{1i}t_{ij}$$

As before, should these models fail to converge, we will allow clinic to remain the random effect, but adjust for baseline LFAZ as a fixed effect.

Extending Model 4 to admit child level covariates, we have:

$$Y_{ij} = \beta_{0_{ci}} + \beta_1 C_i + \beta_2 Z_i \times 1_{\{t > t_0\}} + \beta_3 Z_i t_{ij} \times 1_{\{t > t_0\}} + \beta_4 \mathbf{X}_{ij} + \varepsilon_{ij}$$

- Model 5

Where \mathbf{X}_{ij} is the vector of effect-modifying covariates of child i at time j :

$$\mathbf{X}_{ij} = \begin{cases} \text{age category } (< 6m, 6 - 11m, \geq 12m) \\ \quad + \text{Sex} \\ \quad + \text{Wealth quintile} \end{cases}$$

Where randomization resulted in imbalanced covariates, sensitivity analysis will include in vector \mathbf{X}_{ij} confounders that are imbalanced (e.g. but not limited to: sex, wasting, stunting, dehydration) as previously described.

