9.4.1 Outcome Definitions

1. Δ WLZ = WLZ at endline visit *minus* WLZ at randomization visit
2. Δ WAZ = WAZ at endline visit *minus* WAZ at randomization visit
3. Δ MUAC = MUAC at endline day visit *minus* MUAC at randomization visit

In sensitivity analysis the endline visit date will be restricted to those who had the visit from study day 91 to 100.

The group means for WLZ, WAZ and MUAC at baseline, endline and mean change will be presented by group as indicated in Table 3. We will use generalized linear mixed models with Δ WLZ, Δ WAZ or Δ MUAC as response variables and treatment group and fixed effects for study country and random effects for clinic and child as the explanatory variables. A sensitivity analyses including potential effect modifiers and unbalanced confounders will be done. Modeling will be analogous to Models 3-5 listed in Section 9.2, but where Y_{ij} is Δ WLZ, Δ WAZ or Δ MUAC respectively, in child i at time j .

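### The covariate-adjusted growth model (Model 5) is built on the visit-timing sensitivity model, so adjusted and primary ΔLAZ estimates differ in more than the covariates

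*SAP*

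**What the plan says.** SAP 9.2 gives three growth equations.

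- **Model 3** is primary: country, clinic and child effects and one treatment term.
- **Model 4** handles visits that miss the day-90 window, which stay in the intention-to-treat analysis: "Sensitivity analysis will take account of the time varying nature of this visit by fitting a model". It has two treatment terms, β2·Z and β3·Z·t, both switched off at enrolment by an indicator, and a child-level random slope in t. Time has no fixed effect of its own.
- **Model 5** begins "Extending Model 4 to admit child level covariates, we have" and prints both treatment terms plus β4·X. X holds age, sex and wealth quintile. Imbalanced covariates go into the same vector in sensitivity analysis.

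SAP 9.4.1 carries this to ΔWLZ, ΔWAZ and ΔMUAC: "Modeling will be analogous to Models 3-5 listed in Section 9.2".

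The other outcomes are built differently. For mortality, SAP 9.1 has "Extending Model 1 to admit child level covariates, we have", so Model 2 adds X to the primary model. Model 7 for hospitalization likewise adds X to Model 6. Neither contains a treatment-by-time slope.

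SAP 4.4 then sets a switching rule: "If the point-estimates for the unadjusted and adjusted analyses of the primary outcomes differ by more than 10" percent, the adjusted analysis becomes the primary one.

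**The concern.** An adjusted estimate can be set against an unadjusted one only if both measure the same thing and the models differ in the covariates alone. Here Model 5 differs from Model 3 in X and also in a time interaction and a random slope. Model 5 has two treatment parameters, while SAP Tables 2 and 3 have one effect column. Three things are left open: the origin and unit of t, whether the reported effect is β2 or the effect at day 90, and which of these SAP 4.4 compares.

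The missing common time effect is a separate fault. Visit day enters the fixed part of the model only through Z, so any ordinary drift of LAZ with visit day in the treated arm loads on β3 and looks like a changing azithromycin effect.

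At stake is which ΔLAZ figure is called primary. The SAP Introduction records that the DSMB has already seen a statistically significant LAZ difference, so this choice should be fixed before the code is broken.

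**Working it through.** **Inputs from the documents.** Protocol 10.3: "we will have 90% power to detect at least a 0.04 difference in mean" ΔLAZ, with "standard deviation (SD) of 0.6 in both groups" and "5,750 children per group". Protocol 10.3 assumes 10% loss to follow-up, giving 5,750 × 0.9 = 5,175 per arm. Protocol 6.2 gives the visit window as days 80-100. Alpha is 0.05, two-sided.

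**Assumptions, not in the documents.** Visits are uniform on days 80-100, or a share p of them (5% or 15%) is uniform on days 100-140. Drift g, common to both arms, is 0 or -0.001 LAZ per day. There is one row per child, no clinic effect and a constant true effect of 0.04.

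**The plan's own figure.** n = 2 × 0.6² × (1.960 + 1.282)² / 0.04² = 4,729 per arm, against 4,730 in Protocol Table 1. At 5,175 per arm the Model 3 SE is 0.6 × √(2/5,175) = 0.0118 and power is about 92%.

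**Model 4/5 as written, t in days since enrolment.** Let m and s be the mean and SD of visit day. Placebo supplies a mean; the treated arm supplies an intercept and a slope. Then:

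- E(β2) = δ - g·m, and E(β3) = g.
- SE(β2) = (σ/√n)·√(2 + (m/s)²). Relative to Model 3 this is √((2 + (m/s)²)/2), whatever n and σ are.
- The effect at day 90, β2 + 90·β3, has mean δ + g(90 - m) and SE (σ/√n)·√(2 + ((m - 90)/s)²).
- SE(β3) = σ/(s√n).

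For visits in window, m = 90 and s = 20/√12 = 5.77. The ratio is √((2 + 15.6²)/2) = 11.1 and SE(β2) = 0.131. With g = -0.001, E(β2) = 0.04 + 0.09 = 0.13.

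**How often a 10% comparison fails with no covariate effect at all.** β2 minus the Model 3 estimate equals -β3·m, and β3 is independent of the Model 3 estimate. In window this difference has SD 90 × 0.001445 = 0.130, while the 10% band around 0.04 is ±0.004. The chance of falling inside is about 2 × 0.004 × 0.399/0.130 = 2.5%. For the day-90 effect the difference is β3(90 - m). Evaluating these over the distribution of the Model 3 estimate, N(0.04, 0.0118²), gives:

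| Late share p | m | s | SE β2 (ratio) | β2 differs >10%: g=0 / g=-0.001 | SE at day 90 | Day-90 effect differs >10%: g=0 / g=-0.001 | β3 significant, g=-0.001 |
|---|---|---|---|---|---|---|---|
| 0 | 90 | 5.77 | 0.131 (11.1) | 98% / 98% | 0.0118 | 0% / 0% | 11% |
| 5% | 91.5 | 9.00 | 0.086 (7.3) | 96% / 98% | 0.0119 | 3% / 9% | 19% |
| 15% | 94.5 | 12.77 | 0.063 (5.3) | 95% / 98% | 0.0122 | 21% / 57% | 33% |

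Simulated fits of the same settings agree: 95-99% for β2; for the day-90 effect with late visits, 3-22% without drift and 6-58% with it; a false interaction in 9-34%. The SAP's convergence fallback (baseline LAZ as a fixed effect) does not help β2. With normally distributed visit days of SD 5, 10 and 20 and 5,750 per arm, the 10% comparison fails in 99%, 95% and 91%.

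**After the change.** With X added to Model 3, irrelevant covariates trigger the rule in 0% of trials. Centring t at 90 and adding a common time term restores an SE of about 0.012. A common term without centring does not: SE(β2) is then 0.184 in window.

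**The case against.** A reader might infer that no adjusted growth analysis can give a day-90 effect, and that the switching rule will almost certainly promote an uninformative estimate. The documents do not support that.

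- The day-90 effect is recoverable from Model 5 as β2 + 90·β3, with SE about 0.012. With all visits in window it practically coincides with Model 3.
- The SAP never defines t. Days since enrolment, uncentred, is the natural reading but not a stated one.
- SAP 4.4 names neither Model 5 nor β2. It concerns apparent baseline imbalances associated with the outcome, so without imbalance it supplies nothing to adjust for.
- Model 5 is the only displayed growth equation with X, but not the only adjustment possible: SAP 4.4 plans adjustment without naming a model, and SAP 4.6 and the 9.2 fallback allow baseline LAZ as a covariate.
- Low power for β2 (about 6% at SE 0.131) is not a design quantity, because no test of β2 in Model 5 is planned as primary.
- On non-convergence the fallback removes the random slope.

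All of this stands, and it makes the high failure rate conditional. It does not explain why growth alone has its covariates added to a sensitivity model. Nor does it supply the missing common time effect, which affects the day-90 reading as soon as some visits are late.

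**Conclusion.** The fault is in the printed equations: Model 5 extends Model 4, so the adjusted and primary growth estimates differ in more than X. Its size depends on choices that the SAP leaves open.

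- **β2 reported, t in days since enrolment:** an extrapolation to day 0, with SE about 5-11 times that of Model 3 and a difference above 10% in about 95-99% of trials.
- **Day-90 effect reported:** precision is kept. With 5-15% late visits the difference exceeds 10% in about 3-22% of trials without drift and 6-58% with drift of -0.001 LAZ per day. Under that drift β3 is falsely significant in about 9-34% (visits in window to 15% late), against a nominal 5%.

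These rates rest on assumed visit-day distributions and drift, the planned effect and SD, and 5,175 per arm. Achieved enrolment is not in the documents; the SE ratios do not depend on it. The primary Model 3 result is untouched unless SAP 4.4 is applied to a Model 5 estimate.

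**What to change.** 1. Define Model 5, and its ΔWLZ, ΔWAZ and ΔMUAC analogues, as Model 3 plus β4·X, without Z·t.
2. Keep Z·t in Model 4 only. Define t as days since enrolment minus 90, add a visit-time term common to both arms, and drop the random slope, which at most two visits per child cannot separate from residual error.
3. State that the reported treatment effect is the effect at day 90.
4. Apply the SAP 4.4 comparison only between models that differ in X alone.

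The cost is SAP wording; no data or patients are affected. SAP 6.4 already foresees amendments after the blinded analyses.

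This does not cure the 10% rule itself. With X added to Model 3, 5,750 per arm and a true effect of 0.04, the rule still fires by chance in about 6%, 13-16% and 29% of trials when covariates explain 2%, 5% and 10% of the variance. Under a true null with 5% explained it fires in 74%, because the unadjusted estimate is then close to zero.

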9.3 Analysis of secondary objectives 1, 2 and 3 - Hospitalization

Following an episode of high risk diarrhea without dysentery among children 2 to 23 months of age living in low resource settings who are randomized to receive a 3-day course of azithromycin or placebo, comparison by trial allocation arm of:

1. proportion of children hospitalized or died in the initial 10 days following enrolment.
2. proportion of children hospitalized in the 90 days following enrolment.
3. proportion of children hospitalized or died in the 90 days following enrolment.

Primary event considered will be the first episode of hospitalization per child. Hospitalization rates will be reported by country to understand heterogeneity across sites. Risk ratio will be estimated from a model including trial allocation and country of enrollment. Adjusted analysis will include effect modifying covariates, and sensitivity analysis will include unbalanced potential confounders by trial arm.

Hospitalization data are available as binary outcomes only, and date of hospitalization is missing for all events after 10 days of follow-up. Time to event analysis is not possible for the hospitalization outcome.

Since likelihood of hospitalization may cluster by clinic, the following log-binomial mixed effects model is proposed:

$$\log \Pr(Y_i = 1) = \beta_{0c} + \beta_1 C_i + \beta_2 Z_i \times 1_{\{t>t_0\}} + \varepsilon_i \quad - \text{Model 6}$$

Where

$$Y_i = \begin{cases} 1 & \text{hospitalized at least once by day 180} \\ 0 & \text{not hospitalized} \end{cases}$$

Under this definition we are accounting for clustering at clinic level. The b term is a random effects for the c^{th} clinic, and take account of the variance due to clustering within clinic.

The term $\beta_1 C_i$ is the fixed effect of country, with C_i representing the country of enrolment for child i .

The term $\beta_2 Z_i$ is the fixed effect of azithromycin, with Z_i representing the treatment allocation for child i where

$$Z_i = \begin{cases} 1 & \text{azithromycin} \\ 0 & \text{placebo} \end{cases}$$

The term ε_{ij} is the variance component due to random error for child i at time j .

Adjusted analysis will include individual level effect modifiers, thus:

$$\log \Pr(Y_i = 1) = \beta_{0c} + \beta_1 C_i + \beta_2 Z_i \times 1_{\{t>t_0\}} + \beta_{3X} \mathbf{X}_{ij} + \varepsilon_i \quad - \text{Model 7}$$

Where \mathbf{X}_{ij} is the vector of effect-modifying covariates of child i at time j :

$$\mathbf{X}_{ij} = \begin{cases} \text{age category } (< 6m, 6 - 11m, \geq 12m) \\ \quad + \text{Sex} \\ \quad + \text{Wealth quintile} \end{cases}$$

Where randomization resulted in imbalanced covariates, sensitivity analysis will include in vector \mathbf{X}_{ij} confounders that are imbalanced (e.g. but not limited to: sex, wasting, stunting, dehydration) as previously described.

9.4 Analysis of secondary endpoint 4, 5 & 6

Secondary endpoint 4 & 5: To compare Δ WLZ and Δ MUAC in the 90 days following an episode of high risk diarrhea without dysentery among children 2 to 23 months of age living in low resource settings who are randomized to receive a 3-day course of azithromycin or placebo.

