6.1 Day 45 Follow up

Non-medically trained study personnel will contact study participants, using a method of “light contact” at DAY 45 (range DAY 40 to DAY 50). This will involve contact by phone or in-person contact. The purpose of this contact is to ascertain the vital status of the enrolled child at DAY 45, ascertain any hospital admissions since enrolment, and to remind the caregiver of the DAY 90 follow up. No other outcome determination will be performed at this contact.

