6.2 Day 90 Follow up

At the DAY 90 follow up a standardized assessment will be performed by an appropriate trained staff to ascertain vital status, hospitalizations, and health of the enrolled child, as well as his/her nutritional status (weight, length and MUAC). Participants will be contacted by phone up to three times within the DAY 80 to DAY 100 period to fix an appointment for this DAY 90 follow up visit that will either take place at the health facility (in which case transport will be reimbursed to the caregiver), or at the home of the enrolled child. Anthropometric measurements will be performed by a team of dedicated personnel, trained according to standard procedures (see SOP manual).

Children enrolled in the AMR sub-study will also be asked to provide a stool sample. In addition, a naso-pharyngeal swab will be taken in the same sub-sample of children. These samples will be processed and used to study the emergence of bacterial resistance to antimicrobial agents, as described in more detail in section 6.5 below.

If a child is reported to have died at any time or at the DAY 45 contact or at the DAY 90 visit, or at any other point during the study follow up period, specially trained study staff will review hospital record (if available) and conduct a standardized verbal autopsy interview to ascertain

the date and cause of death. The verbal autopsy effort will include capturing all relevant hospital/facility-based information on a child that dies in a facility.

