7. SERIOUS ADVERSE EVENTS

Serious Adverse Events (SAE) will be recorded from enrolment to DAY 10 (7 days after the end of study intervention). Data on mortality and hospitalizations will be collected until DAY 180.

At enrolment, caregivers will be told to come back to the health facility if the enrolled child present any of the following signs in the following 10 days:

- Anaphylactic reaction, Quincke oedema, convulsions, cutaneous rash, arthralgia, urticaria, and severe colitis.

On DAY 2 and DAY 3 visit for the DOT, the study worker will record any reported SAE.

In case there is a suspected allergic reaction caused by the study drug or other SAE, the participant will not get any further doses of the study drug. In case of a suspected allergic reaction, the study data manager at WHO will break the randomization code for that participant, to know which product the participant was receiving. The data manager will provide this

information to clinicians taking care of the participant, so that they can take into account in the medical management and also counsel the participant's caregivers about any need to avoid certain drugs in future.

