Definition of 180 day Mortality: Death due to any cause occurring ≤ 180 days post-randomization. The day of enrolment in the trial is termed “Study Day 1” therefore 180 days post enrollment is Study Day 181. All deaths or censoring events occurring from enrolment and up to and including Study Day 181 will be included in the primary analysis of the mortality outcome. Deaths and censoring events occurring on or after Study Day 182 (181 days since enrolment) will not be included in the analysis. Other mortality outcomes such as death by day 10 (part of Secondary Outcome 4) and day 90 (part of Secondary Objective 6) will also be defined on basis that day of enrolment is termed “Study Day 1”, making these outcomes on Study Day 11 and 91 respectively.

Date of death:

The date of death may be extracted *in ordered preference* from:

1. Death certificate
2. Hospital or clinic record
3. Caregiver other official written record
4. Caregiver recall

Note that forms do not currently record source of death date. Local SOP's should outline the above ordered preference.

Date of death currently appears on three forms (“Form 08-Vital Status”; “Form 11-SAE”; and on the verbal autopsy form). In cases of conflict among forms, the date appearing on Form 08-Vital Status should be prioritized over other forms.

7.2 Length-for-age Z-score (LAZ):

Length for age will be determined from age, sex, and length information at the date of enrolment (day 1) and date of D 90visit (day 91 up to day 101) of participant age, using the macro developed by the WHO using the WHO 2006 multi-centre growth standard. The LAZ values will be rounded to two decimal points.

7.3 Weight-for-age Z-score (WAZ):

Weight for age will be determined from age, sex, and weight information at the date of enrolment (day 1) and date of final visit (day 91 up to day 101) of participant age, using the macro developed by the WHO using the WHO 2006 multi-centre growth standard. The WAZ values will be rounded to two decimal points.

7.3 Weight-for-length Z-score (WLZ):

Weight for length will be determined from age, sex, length and weight information at the date of enrolment (day 1) and date of final visit (day 91 up to day 101) of participant age, using the macro developed by the WHO using the WHO 2006 multi-centre growth standard. The WLZ values will be rounded to two decimal points.

7.4 Hospitalization:

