First episode of overnight stay in a health facility per child occurring within 10 days from enrolment by trial records

First episode hospitalizations per child occurring within 90 days from enrolment by trial records or parent or caregiver report of overnight stay in a health facility

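### Admissions after day 10 are undated, so the 90-day hospitalization endpoint cannot be cut at 90 days, and its composite joins a visit-based admission cut-off to a fixed death cut-off

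*SAP*

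**What the plan says.** **Definitions.** SAP 7.4 gives two admission windows. The 10-day outcome is "First episode of overnight stay in a health facility per child occurring within 10 days from enrolment by trial records". The 90-day outcome is "First episode hospitalizations per child occurring within 90 days from enrolment by trial records or parent or caregiver report", so caregiver report counts as a source only for the longer window. For deaths, SAP 7.1 takes enrolment as Study Day 1 and cuts at 10 and 90 days, "making these outcomes on Study Day 11 and 91 respectively".

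**Data available.** SAP 9.3 states "Hospitalization data are available as binary outcomes only" and "date of hospitalization is missing for all events after 10 days of follow-up". The only consequence it draws is that time-to-event analysis is impossible. Protocol 6.4 lists date of death for mortality, but only the number and causes of hospitalizations.

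**Contacts.** The DAY 45 contact (DAY 40 to 50) is to "ascertain any hospital admissions since enrolment, and to remind the caregiver of the DAY 90 follow up". For the next visit, Protocol 6.2 says "Participants will be contacted by phone up to three times within the DAY 80 to DAY 100 period", and the Bangladesh, India, Kenya, Malawi, Pakistan and Tanzania plans in Protocol 13 put the visit itself between day 80 and day 100. The DAY 180 contact asks about admissions since the day-90 visit, not since day 90 (Protocol 6.3). Serious adverse events "will be recorded from enrolment to DAY 10 (7 days after the end of study intervention" (Protocol 7).

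**Model.** Model 6 in SAP 9.3 codes the response as at least one admission by day 180. The three objectives it serves concern day 10 and day 90.

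**The concern.** A fixed window needs either dated events or a contact on the closing day. After day 10 the admissions have neither. Their follow-up ends at the visit, which varies by child, while deaths in the same composite end on one fixed Study Day. The reported 90-day proportion would then describe a different quantity from the one defined, and its two components would cover different periods.

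These endpoints carry weight. The SAP version history shows the day-90 composite entering at the review prompted by low mortality, and the SAP introduction reports that recruitment stopped with very few deaths. Readers will look to hospitalization for evidence on serious morbidity.

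The SAP already treats visit timing as an issue for growth: a time-varying model in 9.2, a restricted visit window in 9.4.1 and a per-protocol exclusion in 4.2. It has nothing comparable for hospitalization.

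**Working it through.** The documents give no event rate, sample size or power for any hospitalization endpoint, so there is no figure of the plan to reproduce. The check sets the windows side by side and then sizes the gap under stated assumptions.

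**1. Who is counted in the 90-day composite**

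| Event | Treatment under SAP 7.1, 7.4 and 9.3 |
|---|---|
| Death on Study Day 95 | Dated, after Study Day 91: not counted |
| Admission on Study Day 95, visit on Study Day 98 | Undated, reported at the visit: counted |
| Admission on Study Day 85, visit on Study Day 80 | Not known at the visit; surfaces at DAY 180 without a date |
| Death on Study Day 85, visit on Study Day 80 | Dated, inside the window: counted |
| Admission reported at DAY 40 to 50 | Undated but certainly within 90 days: correctly counted |

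Rows 1 and 2 show the mixed cut-off. Row 3 shows the loss after an early visit. Row 5 limits the problem to admissions first reported at the day-90 visit or later.

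**2. Size of the 90-day spread**

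- Visit at day 80: (80 − 90)/90 = −11%.
- Visit at day 100: (100 − 90)/90 = +11%.

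With a constant hazard, risk by day t = 1 − (1 − p)^(t/90), where p is the true 90-day risk. The values of p are assumptions.

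| p | All visits at day 80 | All visits at day 100 |
|---|---|---|
| 2% | 1.8% | 2.2% |
| 5% | 4.5% | 5.5% |
| 10% | 8.9% | 11.1% (11.05%) |

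These are extremes, since real visits will be spread over the window. If the hazard falls after the acute illness, the range narrows. Visits after day 100 widen it. SAP 9.2 keeps such visits in the growth analysis, but no rule is given for hospitalization.

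**3. The 10-day endpoint**

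The last scheduled contact common to all sites is the DAY 3 dose visit, and the next is at DAY 40 to 50. The gap is 40 − 3 = 37 to 50 − 3 = 47 days. Days 4 to 10 are 7 of the 10 days. The SAP's statement on missing dates concerns events after day 10, so it implies that earlier recorded events are dated and can be classified. The open question is completeness.

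Illustration, with all rates assumed: 5,750 per arm as planned, placebo 10-day risk 2%, true risk ratio 0.70, two-sided 5% level. If a share s of events is captured equally in both arms, the risks become 0.02s and 0.014s. The ratio stays at 0.70.

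| Capture s | Power, placebo risk 1% | 2% | 3% |
|---|---|---|---|
| 100% | 42% | 70% | 87% |
| 80% | 35% | 60% | 78% |
| 60% | 27% | 48% | 66% |

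Recruitment stopped early, so absolute power would be lower if fewer than the planned number were enrolled.

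Adding undated day-45 reports to the 10-day endpoint would not repair this. If a share f of counted placebo events really fell after day 10 and treatment had no effect on them, the observed ratio is (1 − f) × 0.70 + f: 0.73 for f = 10%, 0.775 for 25% and 0.85 for 50%.

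**The case against.** The strongest reply is that the effect is small and the SAP already discloses the missing dates. The visit window is symmetric about day 90, so early and late visits partly offset each other. Admissions reported at DAY 40 to 50 are placed correctly. Allocation is blinded and both arms share one schedule, so misplacement should be mainly non-differential. All of this stands. It limits the damage to the treatment comparison, but it does not make the 90-day rule computable or align the two parts of the composite.

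A reader might infer more, and the documents do not support it:

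- **That the 10-day endpoint cannot be applied.** SAP 9.3 describes dates as missing only after day 10, SAP 7.4 names a source, and serious adverse events are recorded to DAY 10. Deaths run to Study Day 11, so any mismatch with that record is at most about one day.
- **That children have no contact between day 3 and day 45.** Only scheduled contact common to all sites is absent. Caregivers are told to return for listed signs within 10 days and at DAY 5 if the child is not improving (Protocol 5, 5.3.1 and 7), and Malawi encourages a review 5 days later (Protocol 13.4).
- **That dates were never asked for, or that admissions outside study facilities are systematically lost.** The SAP says the dates are missing. It refers to a health facility in general and leaves trial records undefined. The forms and the procedure for serious adverse events are not in the documents.
- **That the 90-day proportion is wrong by 11%.** That figure needs every visit to fall at one end of the window.

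**Conclusion.** The point holds for the 90-day endpoints. As the data stand, the admission endpoint is in effect admission between enrolment and the day-90 visit, and its composite combines that with deaths cut at Study Day 91. The follow-up period for admissions departs from 90 days by at most 11% either way for visits inside the window, and by more if late visits are kept. The likely cost is a mislabelled time horizon and some dilution, with no known direction of bias. This rests on blinding having held and on visit timing being similar in the two arms.

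For the 10-day endpoint the point is narrower. It can be computed from recorded events, but capture on days 4 to 10 is passive and may be incomplete. The documents do not show how incomplete, and the power figures above depend wholly on assumed rates.

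The day-180 coding in Model 6 is a plain inconsistency with the objectives.

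**What to change.** 1. **Protocol 6.1 to 6.4.** Record the date of admission, or the study week if the caregiver is unsure, at the day-45, day-90 and day-180 contacts. At day 180, ask about admissions since the last completed contact. The cost is one field on existing forms plus some recall error. It helps only where contacts are still to be made: the last participants were recruited on 10 July 2019, so their 180 days ended in early January 2020, before the SAP of 12 May 2020.
2. **SAP 7.4 and 9.3, for undated data.** Name the endpoint as at least one admission between enrolment and the day-90 visit. Keep all dated deaths through Study Day 91 in the composite, and state that the admission component has a visit-based cut-off. Moving the death cut-off to the visit date is not a remedy: it would drop a dated death on day 85 after a visit on day 80.
3. **Sensitivity analyses.** Repeat the analysis in a narrow, prespecified band of visits around day 90; restricting to days 80 to 100 would keep the whole spread. Add a bounding analysis that counts, then excludes, admissions first reported at visits after Study Day 91. This bounds the error from late visits only, so the narrow band is needed for early ones.
4. **10-day endpoint.** Report its admission component as admissions detected in trial records, and say which records qualify. Undated day-45 reports should not be added.
5. **Model 6.** Reconcile the day-180 response coding with the day-10 and day-90 objectives.

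Items 2 to 5 cost SAP wording and a few extra model runs. The narrow band reduces the number of children in that sensitivity analysis.
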